6.6.1 Quasi-experimental pre-post study

The sample size for the quasi-experimental pre-post study is calculated separately for each country, based on comparison between pre- and post-intervention periods.. The following assumptions are used:

- ξ power 80%
- ξ alpha 0.05
- ξ pre-intervention referral to a higher level of care 3% (based on informal estimates from country research teams and SPA data from various countries), with a minimum detectable difference of 50%
 - We have chosen a large detectable difference for referral from primary care as not all children referred will complete referral, i.e. a 50% increase in referral rate may only result in a 20 – 30% total increase in completed referrals (this will be assessed as a secondary outcome and is therefore not a component of the sample size calculation)
- ξ pre-intervention antibiotic prescription of 60% (based on informal estimates from countries, SPA data and other observational studies)
- ξ intra-cluster correlation coefficient (ICC) of 0.005 for referral and 0.05 for antimicrobial prescription

- ξ Kenya – estimated average cluster size of 230 children / month (assuming a cluster ratio of health centres : dispensaries 1:2, with 100 / month in dispensaries and 500 / month in health centres)
- ξ Senegal – estimated cluster size of 170 children per month (based on DHIS2 data on outpatient consultations in Thies in 2019)

For the referral primary outcome, we therefore initially estimated requiring the following sample size:

- ξ Kenya – 17 facilities, recruiting an average of 690 children per facility in each period, equating to 11,730 children per period
- ξ Senegal – 18 facilities, recruiting an average of 510 children per facility in each period, equating to 9,180 children per period

For the antibiotic prescription primary outcome, this would enable a minimum detectable reduction of 18% in Kenya and Senegal.

Following lower than anticipated recruitment in the pre-intervention period, sample size calculation was revised. As a result, two additional facilities were added per country and the pre-intervention period was extended from an initially anticipated 3 months to a 6 – 8 month period. A decision was also taken to target a post-intervention sample size of at least the same as the pre-intervention sample size, as well as a minimum duration of 9 months post-intervention to allow for stabilisation over time and some seasonal overlap of pre- and post-intervention periods.

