7.3.1 Quasi-experimental pre-post study

Analysis will include all eligible, consenting and enrolled children. Baseline characteristics will be described by country and across all study time points with summary statistics such as median and interquartile range or number and percentage. Outcomes will be described for each time period using summary statistics and results from the pre-intervention period and the post-intervention period will be compared. The two primary outcomes will be assessed using a random effects logistic regression models with the cluster (facility) included as a random effect. All models will be adjusted for individual-level baseline characteristics such as gender and age whose distribution at the facility may have changed between the time periods. Results will be reported with odds ratios and 95% confidence intervals (CI). Binary secondary outcomes will be evaluated in the same way. Continuous secondary outcomes will be assessed using random effects linear regression models, reporting adjusted mean differences between time periods with 95% CIs.

We will conduct planned subgroup analysis of the primary outcomes to assess for potential effect modification in variables such as clinical presentation (particularly cough / difficulty breathing) and diagnosis (particularly severity classification). If these variables are found to be balanced between the two time periods, effect modification will be assessed by incorporating an interaction between the time period and the variable in the model, acknowledging that power will be low. Additional individual or facility level characteristics to be considered in the model will be further detailed in the statistical analysis plan (SAP).

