4.3 Analysis Populations

All analyses will follow the intention to treat (ITT) principle, irrespective of any protocol violations.

No safety set will be defined but safety information will be reported overall and by use of intervention as defined in section 4.2.

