6.1.2.3 Average length of stay (in days) of children admitted to hospital

Length of stay is defined as hospitalisation duration in days as reported by the caregiver at Day 7. If a child is hospitalised twice, the first hospitalisation will be used and second hospitalisations will be reported separately. The denominator will be all hospitalised children.

6.1.2.4 Proportion of children referred by a primary healthcare provider to a higher level of care at Day 0 consultation

All children who received a referral advice (as per definition above) at Day0 will be counted in the numerator. The denominator will be all children recruited.

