6.1.3 Antibiotic-related outcomes

6.1.3.1 Proportion of children prescribed an antibiotic at Day 0

Information on antibiotics prescription are recorded by the RA on Day 0, after the clinical consultation. The data collection tool is structured in a way to facilitate the reporting of antibiotics, starting with single-drug questions for the most common/important ones to drop-down lists for other antibiotics/treatments and free text. All options will contribute to determine whether an antibiotic prescription was given. A child will be considered prescribed with an antibiotic if:

- ξ “Yes” was selected for at least one single-drug question
- ξ “No” was selected for all single-drug questions but one or more antibiotics were selected from the antibiotics/treatments drop-down list
- ξ “No” was selected for all single-drug questions, antibiotics were not selected from the other antibiotics/treatments drop-down list but antibiotics were listed in the free text field (conditional to feasibility of assessing free text)

All children recruited will be counted in the denominator.

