6.2 Analysis Methods

6.2.1 Analytical Methods

For the primary analysis, pre-intervention and post-intervention periods will be defined as follow:

Pre-intervention period: from the date of data collection start to the date healthcare providers left the facilities for training on the intervention

Post-intervention period: from the date healthcare providers returned to the facilities after training and the devices was delivered to the facilities to the end of data collection

As training was staggered for the facilities, the definitions above will be applied at the facility level.

Outcomes will be described for each time period using summary statistics. In particular, counts and percentages will be used for binary variables and reported with one decimal place; mean and standard deviation (SD) or median (IQR) for continuous variables depending on their

distribution. Mean and median will be displayed with one decimal place and SD and IQR will be presented with two decimal places.

The two primary outcomes will be assessed using a random effects logistic regression model with the cluster included as a random effect. If convergence issues arise due to sparse data, clusters may be dropped or combined to higher grouping level (e.g. district).

Results will be reported with odds ratios, risk differences and their associated 95% confidence intervals (CI).

Secondary outcomes and other binary outcomes of interest will be evaluated in the same way.

Other continuous outcomes of interest will be assessed using random effects linear regression model with the cluster included as a random effect. Results will be reported in terms of adjusted mean differences with associated 95% CIs.

Modelling of secondary outcomes will be performed if numbers allow.

Further exploratory analysis, including interrupted time series analysis to assess change over time and data linked between the quasi-experimental pre-post study and the SPA and time-flow studies. These fall outside the scope of this SAP and will be detailed in a separate document.

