6.2.3 Test of Assumptions, Actions to be taken

Continuous variables will be inspected using histograms: 1) to assess for outliers which may be queried for accuracy, and 2) to assess whether appropriate transformations are required for analyses.

As a multilevel logistic regression model is estimated using quadrature (rather likelihood methods), a quadrature check to test for adequate model fit will be performed. In case of unreliable model fit, generalized estimating equations will be used to fit the model which will provide population-averaged odds ratios and 95% confidence intervals.

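### SAP 6.2.1 allows whole facilities, and so their enrolled children, to be dropped if the primary model does not converge, with no criterion, order or reporting rule

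*SAP*

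**What the plan says.** Protocol 7.3.1 fixes the analysis set and the model. On the set: "Analysis will include all eligible, consenting and enrolled children". On the model: "random effects logistic regression models with the cluster (facility) included as a random effect".

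The SAP repeats the inclusive set. For the referral outcome (SAP 6.1.2.4): "The denominator will be all children recruited". For the antibiotic outcome (SAP 6.1.3.1): "All children recruited will be counted in the denominator". SAP 4.3 adds: "All analyses will follow the intention to treat (ITT) principle, irrespective of any protocol violations".

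SAP 6.2.1 then gives the contingency: "If convergence issues arise due to sparse data, clusters may be dropped or combined to higher grouping level (e.g. district"). It also extends the same modelling to secondary and other binary outcomes, and models secondary outcomes only where numbers permit.

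SAP 6.2.3 has a separate contingency. If the quadrature check shows an unreliable fit, "generalized estimating equations will be used to fit the model which will provide population-averaged odds ratios and 95% confidence intervals".

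The SAP does not say how sparse is judged, which facilities would go, whether merging is tried before dropping, whether removals are reported, or how the 6.2.1 and 6.2.3 fallbacks are ordered.

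**The concern.** Non-convergence shows itself only once the model has been fitted to outcome data. The choice to drop, and which facilities to drop, is therefore made with outcomes in hand, in an open-label study. In a logistic model, sparse most naturally means few events, so the facilities at risk are those with few referrals or complications. Removing them selects on the outcome and leaves a set that is no longer all enrolled children.

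Merging is a different problem. Every child stays in, but the facility random effect is replaced by fewer, larger groups. Correlation within facilities is then unmodelled, and the pre-post contrast is less closely tied to the same facility. That could matter because, after low pre-intervention recruitment, "two additional facilities were added per country and the pre-intervention period was extended", so facilities may differ in their balance of pre and post children.

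**Working it through.** **1. The plan's own figures.** Inputs from Protocol 6.6.1: 3% v 4.5%, 80% power, alpha 0.05 (taken as two-sided), ICC 0.005, and 690 (Kenya) or 510 (Senegal) children per facility per period. The two-proportion formula without continuity correction gives 2,518 per period. The design effect is 1 + (m − 1) × ICC.
- Kenya: 1 + 689 × 0.005 = 4.445; 2,518 × 4.445 = 11,193; ÷ 690 = 16.2, so 17 facilities and 11,730 children.
- Senegal: 1 + 509 × 0.005 = 3.545; 2,518 × 3.545 = 8,926; ÷ 510 = 17.5, so 18 facilities and 9,180 children.

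Both match the protocol. On the same formula, power is 81.8% with 17 facilities and 79.5% with 16 in Kenya, and 81.1% with 18 and 78.9% with 17 in Senegal. This is a guide only, because the formula ignores that pre and post share facilities.

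**2. Can the full-sample referral model be sparse?** Expected referrals per facility per period at 3%: 690 × 0.03 = 20.7; 510 × 0.03 = 15.3; a 300-child dispensary (100 a month for 3 months) 300 × 0.03 = 9. The chance of no referral at a fixed 3% risk is 0.97^300 = 0.0001. I simulated facility risks from a beta distribution (mean 3%, ICC 0.005, risk ratio 1.5), dropping a facility with no event in at least one period. Kenya was set as 11 facilities of 300 and 6 of 1,500. The mean number dropped is 0.05 of 17 in Kenya and 0.01 of 18 in Senegal. Antibiotic prescription at 60% is not sparse.

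**3. Where it can bite** (same simulation; rates and small sizes assumed).
- A 1% outcome at planned sizes: 2.4 of 17 facilities (6.9% of children) dropped in Kenya and 1.9 of 18 (10.3%) in Senegal. The pre-intervention rate among those kept rises from 1.00% to 1.07% and 1.11%.
- 17 facilities with 120 children per period at 3%: 1.2 facilities (7.3% of children) dropped; the rate rises from 3.00% to 3.21%.
- Young infants, if 5% of enrolment: 25.5 to 34.5 per facility per period, with a chance of no referral of 0.97^25.5 = 0.46 to 0.97^34.5 = 0.35.

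**4. Effect on the estimate.** 18 facilities, 25 children per facility per period, 3% to 4.5%, ICC 0.005:

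| Facilities dropped | Mean kept | Pre rate | Risk difference (points) | Odds ratio |
|---|---|---|---|---|
| None | 18 | 3.0% | 1.5 | 1.52 |
| No event across both periods | 14.6 | 3.7% | about 1.85 | 1.53 |
| No event in at least one period | 6.4 | 6.0% | about 1.2 | 1.22 |

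With no true effect, the first dropping rule keeps 13.4 facilities and raises pre and post rates equally, to 4.0%. The risk difference stays at 0.

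**5. Does GEE protect the within-facility contrast?** Assumed case with no true effect: 17 facilities at 3% with 510 children in each period, and two late facilities at 6% with 100 pre and 510 post. Pooled pre rate: (8,670 × 0.03 + 200 × 0.06) / 8,870 = 3.07%. Pooled post rate: (8,670 × 0.03 + 1,020 × 0.06) / 9,690 = 3.32%. The odds ratio is 1.08, which is what an independence working correlation targets; simulated values were 1.08 to 1.10. An exchangeable correlation gave 1.02 to 1.07, depending on the simulation settings, including how much the other facilities vary.

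**The case against.** The strongest reply is that this is a remote contingency. It needs a convergence failure, and a random-intercept model can carry a facility with no events. At planned sizes the full-sample primary outcomes will almost certainly not trigger it, and sparse secondary outcomes may not be modelled at all. The descriptive proportions stay on all recruited children whatever the model does. SAP 6 says young-infant results are presented separately, not that a separate model is fitted, and the 5% share is not in the documents. All of this stands and limits the size of the point. It does not supply a criterion or remove the conflict with the protocol's analysis set.

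Four stronger readings are tempting, and the documents do not support them:
- *That merging also breaches the analysis set.* It removes no child.
- *That the intention-to-treat statement in SAP 4.3 is flatly contradicted.* That sentence concerns protocol violations in a non-randomised study. The firm conflict is with Protocol 7.3.1 and the two denominators.
- *That dropping creates an effect where none exists.* Under no effect the simulated risk difference stays at 0. The distortion appears when there is an effect.
- *That SAP 6.2.1 and 6.2.3 prescribe different actions for the same failure.* Non-convergence and a failed quadrature check can be distinct; only their order is unstated.

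Nor do the documents give start dates or enrolment for the added facilities, so any bias from a changed facility mix cannot be sized.

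**Conclusion.** The point holds for dropping. SAP 6.2.1 permits enrolled children to be removed after outcomes are seen, on an undefined criterion, against an analysis set that admits no such exception. Merging deserves correction for a separate reason: it departs from the protocol's facility random effect.

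The practical risk to the two full-sample primary outcomes is very small at planned sizes. It is larger for rarer binary outcomes, small facilities (SAP 5.2 admits those seeing as few as 20 sick children a month, and recruitment ran below plan) and any model in young infants. There, two plausible readings of sparse move a true 1.5-point risk difference in opposite directions, to about 1.85 or 1.2, and one lowers the odds ratio from 1.52 to 1.22. These sizes rest on the assumed 25 children per facility per period, beta-distributed facility risks and the two dropping rules, none of which the SAP specifies.

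**What to change.** Delete the option to drop clusters from SAP 6.2.1 and replace the sentence with an ordered rule:

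1. If the random-effects model does not converge, fit the GEE of SAP 6.2.3 on all enrolled children, with facility as the cluster, an exchangeable working correlation and a small-sample-corrected robust variance.
2. If that also fails, report only the descriptive pre and post proportions for that outcome.
3. Treat any analysis that drops or merges facilities as a labelled sensitivity analysis, stating the rule used and the number of facilities and children affected.

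The working correlation has to be named, because independence leaves the estimate open to a change in facility mix.

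The cost is a few sentences, using a method the SAP already contains. The odds ratio becomes population-averaged where the fallback is used, some sparse results stay descriptive, and GEE reduces but does not fully remove confounding from a changing facility mix.

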This potential to improve the detection and referral of children with severe disease has led to strengthened interest in the potential to rollout pulse oximetry to primary care. However, before significant investment is made in this area, it is critical to understand what health impact pulse oximetry has, for which children in which contexts, and with what consequences – such as over-referral to already stretched hospital resources. Impact is likely to depend on a number of factors, including burden of hypoxaemia in primary care, choice of criteria for pulse oximetry use (to optimise detection of hypoxaemic children whilst avoiding false positives and over-burdening clinic staff) and pre-existing quality of care.

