6.4 Outcomes

6.4.1 Quasi-experimental pre-post study

Two primary outcomes will be assessed between the pre-intervention and post- intervention period:

- ξ Proportion of children referred by a primary care healthcare provider to a higher level of care (either to a hospital or to an inpatient part of a larger primary healthcare facility) at Day 0 consultation
- ξ Proportion of children prescribed an antibiotic at Day 0 primary care consultation

These two outcomes are selected to reflect the intended impact on referral of children with severe disease (pulse oximetry and CDSA) and antimicrobial stewardship (CDSA). Severe complication outcomes are included in secondary outcomes rather than primary as, given the pre-post nature of the study, change in mortality / morbidity outcomes could be influenced by other events occurring between the baseline and post-intervention comparison phase.

Secondary outcomes:

- ξ Proportion of children with a severe complication (death or secondary hospitalisation) by Day 7
 - Secondary hospitalisation refers to any delayed hospitalisation (occurring at any point greater than 24 hours after Day 0 consultation) and any hospitalisation occurring without referral. The denominator is all enrolled children
- ξ Proportion of children admitted to hospital within 24 hours of the Day 0 primary care consultation and as a result of a referral
 - This is used as a proxy for 'appropriate referral' of children, as those with severe disease should generally be admitted to hospital. The denominator for this outcome is also all children enrolled in the study, rather than only referred children. This is because the proportion of referred children that are admitted may be high in routine care, in the context of an inappropriately low referral rate. The aim of the intervention is therefore to increase the overall referral rate of children with severe disease. Hospital admission is chosen as the proxy of severe disease rather than using primary care classification of severe disease, as there are inadequacies in the classification of severe disease in routine practice
- ξ Proportion of children who completed referral as reported at day 7 follow-up
- ξ Proportion of children cured (defined as caregiver reported recovery from illness) at Day 7 follow-up

Sub-groups for analysis of primary and secondary outcomes:

- ξ Age (under 2 months, 2 – 12 months, 13 – 59 months)
- ξ Sex
- ξ Presentation with cough / difficulty breathing

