3.1.4 Outcomes

This section provides an overview of the outcomes as listed in the protocol.

Primary outcomes

- ξ Proportion of children referred by a primary healthcare provider to a higher level of care at Day 0 consultation
- ξ Proportion of children prescribed an antibiotic at Day 0

Secondary outcomes

- ξ Proportion of children with a severe complication by Day 7
- ξ Proportion of children admitted to hospital within 24 hours of the Day 0 consultation and as a result of a referral (this is a proxy for 'appropriate referral' of children)
- ξ Proportion of children cured at Day 7 follow-up
- ξ Proportion of children who completed referral as reported at Day 7 follow-up

Other outcomes of interest – hypoxaemia (in post-intervention only)

- ξ Proportion of children with severe ($\text{SpO}_2 < 90\%$), moderate ($\text{SpO}_2 90 – 91\%$) and mild ($\text{SpO}_2 92 – 93\%$) hypoxaemia, adjusted for sites at high altitude
- ξ Proportion of children with hypoxaemia (according to differing cut-offs) with severe complication
- ξ Proportion of children with severe hypoxaemia not meeting any other clinical criteria for severe disease
- ξ Proportion of children referred with hypoxaemia who receive oxygen at hospital

Other outcomes of interest – referral and follow-up

- ξ Proportion of children with non-severe disease referred to a higher level of care on Day 0
- ξ Average length of stay (in days) of children admitted to hospital
- ξ Proportion of children attending scheduled follow-up at the same facility by Day 7
- ξ Proportion of children presenting for unscheduled follow-up to any health facility by Day 7

Other outcomes of interest – antimicrobial prescription

- ξ Proportion of children prescribed a diagnosis-appropriate antibiotic
- ξ Proportion of febrile children tested for malaria at Day 0
- ξ Proportion of malaria positive children prescribed an antimalarial
- ξ Proportion of malaria negative children prescribed an antimalarial
- ξ Proportion of untested children prescribed an antimalarial

Other factors for exploratory analyses

- ξ Additional socio-demographic characteristics, urban / rural location, distance from health facility, key household indicators such as maternal age and education
- ξ Main complaint / symptom categories (including cough / difficulty breathing, fever, diarrhoea and other) and time since onset of symptoms
- ξ Alternative hypoxaemia cut-offs
- ξ Health care provider severity classification

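### Length of stay is compared before and after the intervention among admitted children only, so a change in who is admitted can appear as a change in stay

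*SAP*

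**What the plan says.** SAP 3.1.4 lists "Average length of stay (in days) of children admitted to hospital" among the other outcomes of interest for referral and follow-up. It is neither primary nor secondary, and every other outcome in that list is a proportion.

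SAP 6.1.2.3 defines it: "Length of stay is defined as hospitalisation duration in days as reported by the caregiver at Day 7". The first hospitalisation is used, second ones are reported separately, and "The denominator will be all hospitalised children".

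SAP 6.2.1 sets the model for continuous outcomes, "Other continuous outcomes of interest will be assessed using random effects linear regression model with the cluster included as a random effect", and the estimate: "Results will be reported in terms of adjusted mean differences with associated 95% CIs". The sentence does not name length of stay, but nothing else in the list fits it. For models of this kind, Protocol 7.3.1 says the mean difference is between time periods.

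For early admission after referral the protocol took the opposite course on the denominator: "The denominator for this outcome is also all children enrolled in the study, rather than only referred children". Its reason was that the referred subset can look good when referral itself is too low. The SAP gives an all-recruited denominator for early admission (6.1.2.2), completed referral (6.1.2.5) and follow-up visits (6.1.6). It gives none for length of stay.

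**The concern.** Admission is a post-intervention event. Protocol 6.4.1 says the intervention aims to raise referral of children with severe disease, and Protocol 3.1 also raises the possibility of fewer unnecessary admissions. Either way, the children admitted before and after need not be the same kind of child, so a mean difference between them mixes any real change in stay with a change in case mix.

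Three planned features might seem to help, but none removes this:

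- The covariates in SAP 6.2.2 are Day 0 characteristics and may reduce the imbalance. Adding severity at admission would not settle it, because that too is measured after the intervention.
- The transformations in SAP 6.2.3 deal with the shape of the distribution, not selection.
- The hospitalisation sensitivity analyses in SAP 6.2.4 move time cut-offs, not the denominator for stay.

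Protocol 3.1 names "over-referral to already stretched hospital resources" as a consequence to be understood. An adjusted mean difference among admitted children says little about that burden and can move against it.

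**Working it through.** **The plan's own figures.** The documents give no figure for length of stay or overall admission. The sample size can be reproduced and sets the scale. For 3% v 4.5%, two-sided alpha 0.05 and power 80%, the requirement is 2,518 children per period before clustering.

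- Kenya: design effect 1 + 689 × 0.005 = 4.445; 2,518 × 4.445 = 11,193; divided by 690 = 16.2, so 17 facilities and 11,730 children.
- Senegal: design effect 1 + 509 × 0.005 = 3.545; 2,518 × 3.545 = 8,926; divided by 510 = 17.5, so 18 facilities and 9,180 children.

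Both match the protocol. If 1.5% of recruited children were admitted (assumed), Kenya would have about 176 pre-intervention admissions.

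**Inputs for length of stay.**

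- k, the net relative rise in admissions: 0.20–0.30. Protocol 6.6.1 expects that "a 50% increase in referral rate may only result in a 20 – 30% total increase in completed referrals". This is an upper proxy rather than an admission figure, because SAP 6.1.2.5 counts attendance with or without admission.
- L, mean stay of children admitted in either period: 4 days (assumed).
- m, mean stay of the added admissions: varied (assumed).
- No child's own stay changes.

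**Formulas.**

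- Mean stay after = (L + k·m)/(1 + k)
- Difference in mean = k(m − L)/(1 + k)
- Relative change in hospital days per recruited child = k·m/L

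**Results with L = 4.**

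| Added stay m | k | Mean stay after | Difference (days) | Hospital days |
|---|---|---|---|---|
| 2 | 0.10 | 4.2/1.1 = 3.82 | −0.18 | +5% |
| 2 | 0.20 | 4.4/1.2 = 3.67 | −0.33 | +10% |
| 2 | 0.30 | 4.6/1.3 = 3.54 | −0.46 | +15% |
| 4 | 0.20 | 4.8/1.2 = 4.00 | 0 | +20% |
| 6 | 0.20 | 5.2/1.2 = 4.33 | +0.33 | +30% |
| 6 | 0.30 | 5.8/1.3 = 4.46 | +0.46 | +45% |

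With existing/added stays of 4/2, 4/3, 5/2 or 3/1 days and k = 0.20–0.30, the mean falls by 0.17 to 0.69 days while hospital days rise by 7% to 22.5%.

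**Reverse case.** Suppose 20–30% of pre-intervention admissions are 2-day stays that no longer occur, and the rest stay 4 days. Mean stay rises from 0.8 × 4 + 0.2 × 2 = 3.6 (or 0.7 × 4 + 0.3 × 2 = 3.4) to 4.0. Hospital days fall by 11% (3.2/3.6) to 18% (2.8/3.4).

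**Check with a fitted model.** In 200 simulated data sets (17 facilities × 690 per period, 1.5% admitted, k = 0.25, stays 4 and 2 days with SDs 1.5 and 1.0, facility SD 0.3, no covariates), the facility random-intercept model gave a mean difference of −0.38 days. The formula gives 4.5/1.25 − 4 = −0.40. Hospital days per 1,000 recruited rose from 60.2 to 68.0.

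**The case against.** The case against has real force, and most of it limits the point without removing it.

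- **Rank.** Length of stay is one of many other outcomes of interest. No sample size or hypothesis rests on it. This stands.
- **The natural denominator.** Average stay of admitted children is the protocol's named outcome, so admitted children are its proper denominator. This stands for describing it, but not for an adjusted pre/post difference read as an effect.
- **Burden is partly visible elsewhere.** Referral-related admission within 24 hours is reported per recruited child (SAP 6.1.2.2), and secondary hospitalisations as counts and percentages (SAP 6.5). A careful reader could multiply admissions by mean stay. This stands in part: no planned result combines the two, and no caution is planned.
- **Net admissions may not rise by 20–30%.** The denominator also includes secondary hospitalisations, which the programme hopes to reduce. This stands, so the illustration is towards the high end.

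Four stronger readings are tempting but unsupported.

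- A reader might infer that the model must return a spurious effect. It does so only if the added admissions have a different mean stay after adjustment; at m = 4 the difference is zero.
- A reader might infer that the result will point against the burden. That needs milder added admissions. If the intervention mainly adds severe cases, as Protocol 6.4.1 intends, both measures rise.
- A reader might infer that a shorter mean stay would be reported as a saving. No passage says so; Protocol 3.1 does not mention length of stay, and hospital costs are studied separately.
- A reader might infer a known false-positive rate. In the simulation above the difference was significantly negative in 71% of runs. With more skewed stays and 1–2% admitted, an unadjusted comparison gave 13–48%. These rates follow from the assumed spread and from models without the planned covariates, so they should not be quoted as a property of the plan.

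**Conclusion.** The point holds in a limited form. The planned contrast cannot separate a change in stay from a change in who is admitted, and the Day 0 covariates cannot be relied on to do so. With milder added admissions, mean stay falls while hospital days rise; with sicker ones, both rise.

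The direction is algebra: the mean moves with the sign of m − L, and hospital days rise whenever stays are added. The size rests on assumed stay lengths and on a proxy for the rise in admissions. The admission rate scales hospital days per child but not their relative change.

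The consequence is confined to one other outcome of interest. The primary outcomes are unaffected. This is a worthwhile, inexpensive improvement, not a flaw that threatens the study's main conclusions.

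**What to change.** In SAP 6.1.2.3 and 6.2.1:

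1. Keep average length of stay among admitted children as the protocol names it, summarised by period. Do not report an adjusted mean difference as an intervention effect.
2. Add, as the pre/post comparison, hospital days up to Day 7 per 1,000 recruited children, with 0 for children not admitted.
3. State the derivation. Count second admissions, which SAP 6.1.2.3 now reports separately. Cut stays off at Day 7 for children still in hospital at the call. Apply the SAP 6.3 best-case rule to children lost to follow-up, and show loss by period beside the result.
4. Use a confidence interval that respects facility clustering and suits skewed data with many zeros, for example by resampling facilities.
5. Show any admission per recruited child next to it.

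The cost is SAP wording and one derived variable from data the study already plans to collect; the form should be checked to confirm that it records the duration of second admissions. There are two drawbacks. Days beyond Day 7 are not counted. The result also depends on the best-case assumption, so unequal loss between periods would bias it, which is why loss must be shown alongside.
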